research suggesting that antidepressants and psychotherapy have equivalent short-term results for depression, and that psychotherapy better protects against relapse (long-term result).(Schneier et al., 2012)(Lee et al., 2016)(Hien et al., 2015) We propose an effectiveness-implementation hybrid design type III (Curran et al., 2012) (Depression And Primary-care Partnership for Effectiveness-implementation Research [DAPPER]) to determine the outcomes of non-specialist delivered Interpersonal Psychotherapy (IPT) compared to fluoxetine, including assessment of the service delivery mechanism in regards to availability to attend required treatment schedule and affordability.(Obrist et al., 2007)(Penchansky & Thomas, 1981)(Khanassov et al., 2016)(Levesque, Harris, & Russell, 2013)

Preliminary studies

We are currently conducting an effectiveness-implementation hybrid type I study of depression treatment delivered by non-specialists, integrated with HIV care services at a government primary healthcare center (n=300). We have used individual IPT delivered by non-specialist personnel for MDD and Posttraumatic Stress Disorder (PTSD) in three LMICs, including Darfur refugees in Cairo,(Jiang et al., 2014) Sichuan earthquake survivors (absolute risk reduction of greater than 50% and effect sizes of 2.37 (p=0.018) and 1.94 (p=0.056) for MDD and PTSD, respectively)(Jiang et al., 2014) and our current NIMH-funded randomized, controlled effectiveness-implementation hybrid type I trial of IPT for HIV+ women affected by gender based violence integrated within the FACES-supported Kisumu County primary care clinic at Lumumba health center (enrolment complete [n=300], study ongoing).(Zunner et al., 2015)(Onu, [name], Rota, Atewa, & [name], n.d.)

In our current study:

- Clinical outcome domains include mental health (MDD and PTSD diagnostic and symptom measures), HIV (viral load and self-reported anti-retroviral adherence), intimate partner violence, interpersonal functioning, disability, quality of life and neurocognition.

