Hypothesis 1b: Participants who remit with IPT or combination treatment will have fewer relapses over follow-up than those who remit with fluoxetine.

Aim 2:

Investigate key presumed mediators of the relationship between treatment and remission

Hypothesis 2a: For initial treatment with IPT, change in social support will mediate the relationship between treatment and remission—improved social support will be associated with remission

Hypothesis 2b: For initial treatment with fluoxetine, change in emotional reactivity will mediate the relationship between treatment and remission—decreased emotional reactivity will be associated with remission.

Aim 3: Identify demographic and clinical moderators of the relationship between treatment and remission.

Hypothesis 3a: Time or cost for transport between participants' residences and KCH, and other Kisumu County Ministry of Health facilities will moderate the relationship between treatment and remission—higher time/cost will decrease the effect of initial treatment with IPT relative to fluoxetine (more treatment visits required for IPT versus fluoxetine treatment).

Hypothesis 3b: Severity of MDD and/or PTSD symptoms among non-remitters will moderate the relationship between subsequent treatment and remission, such that higher severity will decrease the effect of treatment on remission for treatment switch relative to treatment combination.

Hypothesis 3c: Q learning will produce personalized treatment algorithms using the above or other moderators.

Aim 4. Estimate the costs and cost-benefit ratios for fluoxetine and IPT treatment of depression and PTSD.

Hypothesis 4a: Pooled cost-benefit ratios will show that depression and/or PTSD treatment leads to net economic gain for individuals and households at month 6;

Hypothesis 4b: Separate analyses will find that IPT has a more favorable cost-benefit than fluoxetine at month 30.

Aim 5. Determine the acceptability and feasibility of delivering SMART-DAPPER treatments by telephone.

Hypothesis 5a. Telephone IPT will be acceptable and feasible.

Hypothesis 5b. Telephone fluoxetine provider appointments will be acceptable and feasible.

Aim 6. Determine the effect of telephone treatment delivery on retention in care.

Hypothesis 6a. Participants who elect to receive telephone treatment will have higher retention in care than those who receive face-to-face care.

Significance

The results of the proposed research will be significant in two ways:

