Leveraging the Depression And Primary-care Partnership for Effectiveness-implementation Research (DAPPER) – will be initially randomized to 12 weekly one-hour sessions of IPT (3 months) or 6 months of fluoxetine (tapering up to 60mg). Those participants who are not in remission with at the conclusion of initial treatment will be re-randomized to second-line treatment (see below). Prior to randomization, participants will be given the option to receive their treatment at the health facility or by telephone.

Participants who are randomized to fluoxetine and conduct their visits by telephone will need to collect their medication at the health facility. If participants do not collect their medication at the health facility, fluoxetine may be delivered to participants in the community. A smaller, Part 2, of the study will consist of qualitative interviews and focus groups to assess the overall implementation strategy and gather feedback on the specific interventions. Please see "Part 2," below (and additional consent for this aspect of the study, attached).

Randomization and blinding: Randomization will take place after baseline measures are complete. Randomization will be done in blocks of 10 and stratified by sex and telephone vs in-person treatment to ensure that the treatment groups are approximately equal in size and in gender distribution and telephone vs in-person treatment. See below

for second randomization information. Clinical evaluators who conduct follow-up assessments will be blinded to treatment assignment. Participants, IPT therapists, fluoxetine providers cannot be blinded because they will either be providing or receiving the IPT and/or Fluoxetine treatment and therefore they will know their treatment status. In addition, at least one study coordinator will not be blinded to assist with tracking of participants.

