Study visits: To characterize the trajectory of symptom change during treatment, participants will be re-evaluated at the mid-point of treatment (month 1.5 for IPT and month 3 for fluoxetine). Treatment mid-point data is valuable because it can inform the minimum duration of treatment necessary to optimize mental health gains in a setting of scarce mental health resources. For example, if 90% of all observed treatment gains are achieved in the first half of treatment, subsequent implementation efforts might consider shortened courses of treatment. Participants will be assessed at month 3 (end of IPT treatment, mid-point of fluoxetine treatment) and at month 6 (end of fluoxetine treatment). For those participants who are in remission from depression and/or PTSD, follow up assessments will then continue at 9 month, 12 month and then at six month intervals until month 30 to assess for maintenance of gains and relapse. Assessments may be done at the health facility or by telephone. We are defining remission as absence of disease as defined by threshold criteria for Diagnostic and Statistical Manual of Mental Disorders-V (DSM-V) for PTSD and MDD. Those participants who have not yet remitted will be re-randomized to: switch of treatment (from IPT to fluoxetine or vice versa) or combination treatment (addition of IPT to fluoxetine or vice versa). See Figure 3.

Assessment schedule and rationale:

In order to characterize the trajectory of symptom change during treatment, participants will be re-evaluated at the mid-point of treatment (month 1.5 for IPT and month 3 for fluoxetine). Treatment mid-point data is valuable because it can inform the minimum duration of treatment necessary to optimize mental health gains in a setting of scarce mental health resources. For example, if 90% of all observed treatment gains are achieved by month 1.5, subsequent implementation efforts might consider shortened courses of treatment. Participants will be assessed at end of treatment (month 3 for IPT and month 6 for fluoxetine) and fluoxetine recipients will be tapered off the medication. At six months, participants will be re-assessed and then monitored at 6-month intervals until month 30 (Figure 3). Assessment visits may be done at the health facility or over the telephone.

Measures (Table 1): *Demographics.* We will obtain usual demographic measures, education, including individual income, assets, education and school fees, healthcare utilization, and time allocation.

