Data collection. Data collection will use tablets programmed with Research Electronic Data Capture (REDCap), similar to the electronic data system that we are currently using in Kisumu, Kenya (Online Data Kit [ODK]). REDCap now has an offline feature which does not require internet connectivity for data entry and can be later connected to the internet for upload to secure server.

Effectiveness outcomes

Clinical evaluators. Clinical evaluators will consent and screen study participants, complete baseline measures and then refer participants to (un-blinded) study coordinators for randomization. Blinded to group assignment, clinical evaluators will conduct 1.5 month (IPT treatment mid-point), 3 month (IPT end-of-treatment, fluoxetine-mid-treatment), and follow-up assessments. Candidate clinical evaluators will undergo a two day training during which they will be introduced to the study measures and their proper application. At the conclusion of the training, the candidates will be observed in their administration of the measures, assessing for accuracy and completeness. If successful, they will be evaluated for reliability by conducting a group interview and comparing measure results. Those who demonstrate both accuracy and inter-rater reliability will be invited to join the study. Monetary compensation will be provided for completed measures at the local currency equivalent of 7usd.

Data analysis plan

For *Hypothesis 1a* the analysis is standard intention to treat for 3 month (end of treatment) data. Our basic analysis strategy will be to fit logistic regression models for the outcome of MDD and/or PTSD remission, in this case with the predictor of group assignment (IPT or fluoxetine), demographics and severity of baseline depression and/or PTSD symptoms (BDI and PCL) . *Hypothesis 1b* will be analyzed for the sub-group of participants who are in remission from MDD and/or PTSD at months 1.5 or 1.5 and 3 and will use weighted generalized estimating equations logistic regression to accommodate the repeated measures on this subgroup through month 30.

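### Hypothesis 1b compares relapse by the treatment on which people remitted, so the contrast is not randomised and mixes treatment lines, and the stated analysis set cannot test its combination part

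*Protocol*

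**What the plan says.** Hypothesis 1b (protocol, Hypothesis and Specific Aims) reads: "Participants who remit with IPT or combination treatment will have fewer relapses over follow-up than those who remit with fluoxetine".

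The design has two randomisations. Under Study Procedures, participants "will be initially randomized to 12 weekly one-hour sessions of IPT (3 months) or 6 months of fluoxetine"; there is no first-line combination arm. The second stage is for first-line non-remitters only: "Those participants who are not in remission with at the conclusion of initial treatment will be re-randomized to second-line treatment". Study visits gives the options: "Those participants who have not yet remitted will be re-randomized to: switch of treatment (from IPT to fluoxetine or vice versa) or combination treatment".

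The Data analysis plan restricts 1b to people in remission at months 1.5 or 1.5 and 3, and uses "weighted generalized estimating equations logistic regression to accommodate the repeated measures on this subgroup through month 30". It defines neither the weights nor the group variable. Table 2, row 3, describes maintenance of month-3 remissions on IPT and month-6 remissions on fluoxetine. Sample size calculations likewise speaks of relapse after remission on initial treatment. The SAP compares switch with combination on MDD, PTSD, BDI-2 and PCL-5, but contains no relapse analysis.

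**The concern.** The hypothesis and the design do not fit together, for three reasons.

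1. **Line of treatment.** Every combination remitter has already failed a full first-line course. Pooling them with IPT remitters and comparing the pool with fluoxetine remitters puts unequal shares of first-line failures on the two sides.
2. **Prior treatment.** People who remit on fluoxetine can include those switched to it after a course of IPT, and people who remit on IPT can include those switched from fluoxetine. The Background section's premise is that psychotherapy protects better against relapse. If so, any lasting effect of IPT in the first of these flows sits in the comparator.
3. **Selection on an outcome.** Remission occurs after randomisation. If the arms differ in how many or which people remit, their remitters differ in prognosis.

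At stake is the trial's long-term claim, for which follow-up runs to month 30. The two randomisations could support such a claim, but 1b uses neither of them.

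**Working it through.** **The plan's own figures.** No sample size, power or relapse rate is given for 1b. The second-stage figures set the group sizes, so I checked those first. Per-group n = 2(z₀.₉₇₅ + z₀.₈₀)²/d².
- d = 0.31 gives 164 (stated 164).
- An odds ratio of 1.59 gives d = ln(1.59) × √3/π = 0.2557 and n = 241 (stated 242, which agrees within rounding).
- 242 × 4 = 968, and 968/0.5 = 1936, as stated.

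**Who would be in each 1b group as worded.** Of 1936, half remit at first line: 968, or 484 per arm. The other 968 split into four second-line arms of 242. Let r be second-line remission. The documents do not give it, so I assume 50%, with a range of 30% to 66%.
- Fluoxetine remitters: 484 + 242r = 605, of whom 121 (20%) failed IPT first. Range 13% to 25%.
- IPT-or-combination remitters: 484 + 3 × 242r = 847, of whom 363 (43%) failed first-line treatment. Range 31% to 50%. The 363 are 242 combination remitters and 121 switched from fluoxetine to IPT.

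**Spurious gap with no treatment effect on relapse.** Assume one severity factor u ~ N(0,1), with logit P(remit) = a − bu and logit P(relapse) = c + bu. Set a for 50% remission at each line and c for 30% relapse overall, and take b = 0.5 or 1.0. The slopes and the 30% are assumptions.

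| | b = 0.5 | b = 1.0 |
|---|---|---|
| First-line remitters relapsing | 27.6% | 22.6% |
| Second-line remitters relapsing | 30.0% | 30.3% |
| 1b fluoxetine group | 28.1% | 24.2% |
| 1b IPT-or-combination group | 28.7% | 25.9% |
| Odds ratio, 1b groups | 1.03 | 1.10 |

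The 1b gap is the difference in first-line-failure shares times the difference between lines: (0.429 − 0.200) × 2.4 = 0.55 points, and 0.229 × 7.7 = 1.76 points. From the tabulated group rates this is about 0.5 to 1.7 points.

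**Sensitivity.** Suppose instead that first-line remitters relapse at 30% and second-line remitters at k times that rate, whatever the treatment. Group relapse is then 30% × [1 + (k − 1) × share]. At r = 50%, fluoxetine versus IPT-or-combination is:
- k = 1.25: 31.5% v 33.2%
- k = 1.5: 33.0% v 36.4%
- k = 2: 36.0% v 42.9%

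Over r = 30% to 66% and these k, the gap is 1.4 to 7.5 points, in the same direction.

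**Unequal first-line remission.** In the severity model, remission of 38% versus 66% gives relapse among remitters of 27.1% v 28.4% (b = 0.5) or 21.1% v 24.7% (b = 1.0). The arm with less remission looks better on relapse, so the direction depends on which arm that is.

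**Analysis set in the Data analysis plan.** Second-line treatment starts after month 3 (IPT-first) or month 6 (fluoxetine-first), so it cannot have produced a remission at month 1.5 or 3. In that set the first-line-failure share is 0% on both sides and there are no combination remitters. Selection on remission remains. In addition, month 3 is the end of IPT but the midpoint of fluoxetine.

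**The case against.** The strongest reply is that the planned analysis is not the contrast as worded. The Data analysis plan, Table 2 (row 3) and Sample size calculations all tie relapse to first-line remission, which removes the line mixing and the switchers. That is right, and a reader who infers that the planned fluoxetine group will contain IPT completers goes further than the documents allow. It does not rescue the hypothesis: the combination part cannot then be tested, and the groups are still selected by remission.

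A reader might also take the contrast between lines (odds ratios of about 1.12 and 1.5 in the model above) as the bias in 1b. It is not, because both 1b groups mix lines. Nor do the documents support saying that a finding in favour of 1b could come entirely from line mixing. Under these assumptions line mixing runs against 1b and would mask a benefit rather than create one.

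The 38% and 66% pair is not a forecast. The figures come from different populations and treatment durations (12-week IPT in HIV-positive women in Kisumu; a 9-month antidepressant course in Uganda). Sample size calculations puts Kisumu IPT remission above two-thirds, and Hypothesis 1a expects similar remission. The pair shows only that unequal remission can bias either way.

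Finally, relapse among remitters is a fair clinical question, and the SAP's primary tests do not involve 1b. Both points stand and limit the severity.

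**Conclusion.** The concern holds for Hypothesis 1b as worded: the contrast is not randomised, and it mixes line of treatment and prior treatment with the treatment compared. The imbalance in first-line failures, 43% against 20%, follows from the protocol's 50% first-line remission and an assumed 50% at second line. The resulting spurious gap is small under the severity model (about 0.5 to 1.7 points against 1b). It is larger only if second-line remitters are assumed outright to relapse much more often. No document gives a relapse rate, so none of these sizes is a prediction. The conclusion does not rest on them, because a larger sample would not turn this contrast into a treatment effect.

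The stated analysis set avoids the mixing but leaves the combination claim untested and still conditions on remission. Hypothesis and analysis therefore answer different questions. This is a should-fix. It does not undermine the first-line or second-line comparisons in the SAP.

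**What to change.** Reconcile Hypothesis 1b, the Data analysis plan, Table 2 (row 3) and Sample size calculations, and add the relapse analysis to the SAP. Split 1b along the two randomisations:

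- **(a) First randomisation.** IPT-first versus fluoxetine-first in all randomised participants. The outcome is remission after first-line treatment, sustained without relapse to a fixed month from the first randomisation, such as month 30. State that remission gained only at second line does not count here. First-line treatment ends at month 3 or month 6, so remission must hold for 30 − 3 = 27 or 30 − 6 = 24 months; say so when reporting.
- **(b) Second randomisation.** Combination versus switch in all re-randomised non-remitters, within first-line arm. The outcome is sustained remission to a fixed time from re-randomisation.

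Handle missing follow-up by multiple imputation, as the SAP does for BDI-2 and PCL-5. Counting dropouts as failures should be a sensitivity analysis only, since the protocol allows for 40% dropout and that rule would let dropout dominate the outcome.

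Keep relapse among remitters as a secondary comparison. Label it non-randomised, report it separately by line of treatment, adjust it for baseline BDI and PCL, and define its weights and group variable.

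The cost is rewording and two extra analyses of data already scheduled for collection. The downside is that the all-randomised outcome combines remission with relapse, so it should be reported beside the remitters-only result.

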Project Title: SMART-DAPPER: Leveraging the Depression And Primary-care Partnership for Effectiveness-implementation Research Project (SMART-DAPPER)

Clinicaltrials.gov number: NCT03466346

Title of Document: Protocol (version 7.0)

Date of Document: October 27, 2021

**A SEQUENTIAL, MULTIPLE ASSIGNMENT RANDOMIZED TRIAL
(SMART) FOR NON-SPECIALIST TREATMENT OF COMMON
MENTAL DISORDERS IN KENYA: LEVERAGING THE DEPRESSION
AND PRIMARY-CARE PARTNERSHIP FOR EFFECTIVENESS-
IMPLEMENTATION RESEARCH (DAPPER) PROJECT (SMART-
DAPPER)**

By

[name] MMed (Psychiatry) PhD

[name] [name]

[name] MMed (Psychiatry)

© October 2021

ABSTRACT

Introduction:

Dominated by depression, mental disorders are a leading cause of global disability. Most of the disease burden is in Low and Middle Income Countries (LMICs), where 75% of adults with mental disorders have no service access. Despite nearly 15 years of efficacy studies showing that local non-specialists can provide evidence-based care for depression in LMICs, few studies have advanced to implementation research. As emphasized by a recent World Health Organization (WHO) initiative, integration of depression treatment into existing systems of care is critical to achieving public health impact. Kenyan leaders recently launched an initiative to scale-up treatment for mental disorders in primary healthcare, prioritizing depression. Yet, they lack an evidence base for the two essential treatments – psychotherapy and second-generation antidepressants - without which the scale-up will fall short of its potential. The proposed research responds to this need and builds on our current work in Kisumu, showing that Interpersonal Psychotherapy (IPT) can be delivered by trained non-specialists with high efficacy for the treatment of depression and/or PTSD using fluoxetine or Interpersonal therapy. In the context of the ongoing COVID-19 pandemic, and to adequately respond to and provide additional care for new or worsening mental health needs, we will integrate a phone based screening, assessment and treatment options. Additionally, the study applies a SMART design to manage non-responsiveness to the given treatment by switching or combination.

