In light of the COVID-19 pandemic, Kenya has appropriately responded with strict stay-home and curfew orders to limit transmission. Yet, these restrictions are likely to worsen symptoms for those already living with Major Depressive Disorder (MDD) and Posttraumatic Stress Disorder (PTSD), the focus of SMART-DAPPER treatment. In order to adapt to the community's mental health care implementation needs, participants will have the option to have their treatment visits (Interpersonal Psychotherapy [IPT] and fluoxetine initiation and management) and assessment visits by telephone.

Prior to randomization, participants will choose if they would prefer to receive their treatment at the health facility in person or by telephone. Participants who are randomized to fluoxetine will collect their medication at the health facility. If

participants do not collect their medication at the health facility, fluoxetine may be delivered to participants in the community.

[figure not shown]
RESEARCH METHODOLOGY AND PROCEDURES

Study location:

Kisumu County is in western Kenya near Lake Victoria and the county capital is Kisumu, the third largest city in Kenya. With its high prevalence of HIV, the region has been a focus of national and international healthcare efforts, with robust research infrastructure (Figure 1).

Kisumu County Hospital is a county government run facility situated at the centre of Kisumu city, just next to Kisumu Bus Park. The facility still hosts the only county psychiatric ward, which serves the whole former Nyanza region. The outpatient department is headed by a physician, 2 Medical Officers, 3 Clinical Officers and Nurses. On estimate 10,000 adult primary care outpatients are seen per month.

Figure 1: Map of study area

Kisumu County Hospital (KCH):
10,000 adult primary care outpatients seen per month

Study Design:

Effectiveness-implementation study designs are a transformative tool for making evidence-based depression care disorders equitably available in LMICs. Recently, Curran

and colleagues defined effectiveness-implementation hybrid study designs.(Curran et al., 2012) These designs include both effectiveness and implementation outcomes, allowing for the collection of data on individual clinical outcomes as well as system-level data on provider training, supervision, financing and workflow in real-world settings.

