therapist (see therapist selection and training procedures, above), in 12 weekly 60-minute sessions. Participants randomized to receive fluoxetine will meet or speak with fluoxetine trained provider at baseline, 2 weeks, 4 weeks, 2, 3, 4, 5, and 6 months, for a total of eight appointments. Participants will be assessed for initiation of fluoxetine and advisement on common side effects. Fluoxetine participants will be started on 20mg (1 capsule per day) and will return for assessment of initial efficacy/tolerability at week 2. If the participant does not have any prohibitive side effects, dose will be maintained at 20mg (1 capsule). Participant will return for re-assessment at week 4, if the participant does not have any prohibitive side effects and does not have improvement on the Patient Health Questionnaire-2 (PHQ-2), dose will be increased to 40mg (2 capsule). At month 2, if the participant does not have any prohibitive side effects and does not have improvement on the PHQ-2, the dose will be increased to 60mg (3 capsule). Participants receiving treatment by telephone may be able to receive a 3 month supply at the minimum dose (20 mg per day). If the dose is increased during the intervening treatment visits, the participant will need to receive additional medication. Participants receiving treatment by telephone will be asked to pick up their medication within two days of their treatment call. If they do not collect their medication within 2 days, the medication will be delivered in the community. Studies support that higher fluoxetine doses do not show additional benefit.(Jakubovski, Varigonda, Freemantle, Taylor, & Bloch, 2016) See Protection of Human Subjects section for details on fluoxetine side effect management. The participant will be maintained at 20, 40 or 60 mg at the month 3, 4, and 5 visits, if the participant does not have any prohibitive side effects. At the month 6 visit, participants will be given instructions for tapering off fluoxetine, with decrease of the dose by 20mg

increments each week until reaching zero. Participants who were maintained on 20 mgs throughout the treatment period will have fluoxetine discontinued at the end of 6 months. IPT therapists and fluoxetine-trained providers will be compensated per IPT/medication session/day completed, at the local currency equivalent of 10usd.

Fluoxetine treatment duration: Participants treated with fluoxetine will be tapered off fluoxetine at month 6.

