Retention: Based on previous work, retention is not expected to be a problem. Our pilot study of IPT for Sudanese refugees in Cairo had a 93% retention rate; our study of IPT for survivors of the Sichuan earthquake had an 85% retention rate and our ongoing study of integrated IPT care with HIV+GBV+ women in Kisumu has 300 enrollees with 20 dropouts (93% retention, to date). However, given uncertainty regarding generalizability to the KCH and other Kisumu County Ministry of Health facilities adult primary care clinics, the more conservative estimate of 20% drop-out will be used. However, provision of treatment over the telephone may improve retention rates. As part of retention efforts, participants will be asked to provide the name and phone number of a trusted adult who can be contacted if the study has concerns about participants' welfare or whereabouts. Therapists and fluoxetine providers will be asked to provide study cell phone numbers to study participants. Missed appointments will be followed with at least two efforts to reach the participant directly and/or through their contact (80% cell phone coverage). Likewise, at least two efforts will be made to reach drop-out participants for remaining measures.

Acute mental health care: IPT therapist and fluoxetine training will include risk assessment and referral procedures for acute mental health care needs. See Protection of Human Subjects section for details.

Clinical evaluators: Clinical evaluators will be blind to treatment group and will conduct baseline screening at the primary care clinic prior to initiating treatment, as well as re-assessments at months 1.5 (mid-treatment for IPT), 3 (mid-treatment for fluoxetine), 6, 9 month 12, 18, 24 and 30. Candidate clinical evaluators will undergo a two day training during which they will be introduced to the study measures and their proper application. At the conclusion of the training, the candidates will be observed in their administration of the measures, assessing for accuracy and completeness. If successful, they will be evaluated for reliability by conducting a group interview and comparing measure results. Those who demonstrate both accuracy and inter-rater reliability will be invited to join the study. Monetary compensation will be provided for completed measures at the local currency equivalent of 7usd.

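### Aim 6 is worded as an effect of telephone delivery, but Hypothesis 6a compares self-selected groups, and no adjusted or concurrent comparison is planned

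*Protocol*

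**What the plan says.** Under Hypothesis and Specific Aims, the protocol words Aim 6 causally: "Determine the effect of telephone treatment delivery on retention in care". Hypothesis 6a then states the comparison: "Participants who elect to receive telephone treatment will have higher retention in care than those who receive face-to-face care".

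The end of the Literature Review says how mode is assigned: "Prior to randomization, participants will choose if they would prefer to receive their treatment at the health facility in person or by telephone". Study Procedures repeats that the option is given before randomisation. Under Randomization and blinding, mode appears only as a stratum: "Randomization will be done in blocks of 10 and stratified by sex and telephone vs in-person treatment".

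The Abstract introduces telephone care as a pandemic measure ("In the context of the ongoing COVID-19 pandemic, and to adequately respond to" new or worsening mental health needs). The Literature Review gives the setting: "Kenya has appropriately responded with strict stay-home and curfew orders to limit transmission". No start date for the telephone option is given.

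The Retention paragraph expects a benefit without giving a size: "However, provision of treatment over the telephone may improve retention rates". The treatment schedule section says that telephone fluoxetine participants may receive a three-month supply at the minimum dose, and adds: "If they do not collect their medication within 2 days, the medication will be delivered in the community".

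The protocol's Data analysis plan, its Feasibility and Fidelity text and the SAP contain no model, covariate set, comparison set or caveat for Aim 6. Retention in care is not defined for this aim.

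**The concern.** An effect of telephone delivery on retention requires groups that would have been retained equally under the same mode. Here the groups are formed by choice. Anything that influences both the choice of telephone and the likelihood of staying in care will appear in the comparison as if it were due to telephone.

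The documents name plausible candidates. The Feasibility paragraph lists lost wages, dependent care and transport burden among reasons for attrition, and these are also natural reasons to prefer telephone. The inclusion criteria accept ability to attend in person or by telephone, so someone who can attend only by telephone can enter only that group. The Retention paragraph relies on phones to trace people who miss appointments, so phone access may affect both the choice and the tracing.

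What is at stake is the interpretation of one implementation aim. As worded, a difference between the groups would be reported as an effect, although the design supports only an association.

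**Working it through.** **Plan's own figure.** There is none. The documents give no effect size, telephone share, sample size or power for Aim 6, so there is nothing to reproduce.

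**Reading the text side by side.**
1. The aim is an effect of mode on retention.
2. The contrast is elected telephone versus face-to-face.
3. Assignment is by participant choice before randomisation. Stratifying by mode balances IPT and fluoxetine within each mode. It does nothing to make telephone and in-person participants alike.
4. The Data analysis plan specifies adjusted logistic regression for Hypothesis 1a remission. The Feasibility and Fidelity text offers means and proportions with 95% confidence intervals. The SAP's GEE models contain time, intervention group and their interaction. None has retention as outcome with mode as predictor, and none has a calendar term.
5. No rule says whether people enrolled before telephone was offered count as face-to-face, or how people who change mode are classified.

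**Illustration of possible size (assumed inputs).** Suppose telephone has no effect, and one unadjusted factor raises retention by *g* and is more common among choosers by Δ. The spurious difference is *b* = *g* × Δ. With *g* from 10 to 20 points and Δ from 20 to 40 points, *b* runs from 0.10 × 0.20 = 2 points to 0.20 × 0.40 = 8 points.

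Other inputs:
- N = 2710 (Sample size calculations), or 1000 (assumed) for a restricted set.
- Overall retention *R* of 80% (20% drop-out in the Retention paragraph) or 60% (40% drop-out in Sample size calculations).
- Telephone share *s* of 10% to 50% (assumed).
- Two-sided alpha of 0.05, the level the protocol uses for its sample size.

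Formula: in-person retention p₀ = R − s·b, telephone retention p₁ = p₀ + b, and

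P(test favours telephone) = Φ[(b − 1.96·SE₀)/SE₁],

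where SE₀ is the pooled and SE₁ the unpooled standard error.

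Worked case, R = 0.80, s = 0.30, N = 2710 (813 telephone, 1897 in person), b = 0.04:
- p₀ = 0.788, p₁ = 0.828.
- SE₀ = √[0.16 × (1/1897 + 1/813)] = 0.01677.
- SE₁ = √[0.788 × 0.212/1897 + 0.828 × 0.172/813] = 0.01622.
- (0.04 − 1.96 × 0.01677)/0.01622 = 0.44, so P is about 67%.

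Probability of a result favouring telephone when it has no effect, at a 30% telephone share:

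| Retention | N | b = 2 points | b = 4 points | b = 8 points |
|---|---|---|---|---|
| 80% | 2710 | 21.8% | 67.0% | 99.9% |
| 80% | 1000 | 10.5% | 29.9% | 84.3% |
| 60% | 2710 | 16.1% | 49.5% | 97.6% |
| 60% | 1000 | 8.5% | 21.7% | 66.1% |

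Over the whole grid, including telephone shares of 10% and 50%, the range is 5.7% to 99.9%, against a nominal 2.5% in that direction. If the factor instead lowered retention among choosers, the bias would run against telephone. The width of the range shows that the documents do not fix the answer.

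**The case against.** The case on the other side has several parts.

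- Hypothesis 6a says openly that participants elect telephone, so only the aim's heading is causal. This is largely right, and it makes the rewording small. But the heading is the aim the hypothesis is meant to serve, and no caveat joins the two.
- An unadjusted test should not be presumed, because the regression described for Hypothesis 1a includes demographics and baseline severity. That is fair as far as it goes. The text is not extended to Aim 6, and those covariates omit travel cost, opportunity cost and enrolment date.
- A reader might infer that calendar period does confound the comparison. The documents do not show this. The telephone start is undated, and the text can be read as offering every participant the choice. Calendar confounding is conditional on how earlier enrollees are counted.
- A reader might also take it as established that choosers differ, or that telephone would be flattered. The first is a well-grounded expectation but not a documented fact. The second does not follow: phone access could favour telephone, while people with heavy travel burden might choose it and be harder to keep.
- The policy menu described under Significance concerns cost-benefit options and does not mention telephone, so a misleading policy message is not something the documents announce.
- This is one of six aims in a type I hybrid that puts clinical effectiveness first. That stands, and it limits the weight of the point.

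**Conclusion.** The point holds in a limited form. The stated contrast cannot answer Aim 6 as worded, because mode is self-selected and no adjusted or concurrent comparison is planned. It is open to confounding by factors such as travel cost and lost wages and, if pre-telephone enrollees count as face-to-face, by calendar period. The size and direction of bias cannot be derived from the documents. The range of about 6% to 99.9% rests entirely on assumed prevalence gaps, retention effects and telephone shares, and no single value in it should be quoted alone.

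Adjustment cannot fully repair this. Table 1 has telephone costs but no measure of phone access, and the supply and delivery arrangements for telephone fluoxetine participants mean that even a well-adjusted contrast describes a package. The reworded claim must carry most of the weight.

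The randomised comparisons, IPT versus fluoxetine and switch versus combination, are not affected. The change is worth making but is not critical to the trial's main results.

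**What to change.** 1. Reword Aim 6 as the association between elected telephone delivery and retention. State that telephone is a package that includes the medication supply and delivery arrangements in the treatment schedule section. The Literature Review mentions community delivery for fluoxetine participants without limiting it to telephone, so say which group it applies to.
2. Define retention in care for this aim, including its time window.
3. Restrict the comparison to participants enrolled while both modes were offered, and give the date on which telephone opened. Classify participants by the mode chosen before randomisation, whatever they later used.
4. Adjust by regression or propensity weighting for enrolment date, transport cost, proximity, opportunity cost, income, baseline BDI and PCL-5, sex and treatment arm. Apart from enrolment date and arm, which the trial records will hold, and sex, which is already a stratification factor, these are Table 1 measures.
5. Add a sensitivity analysis for unmeasured confounding, naming phone access.

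The cost is a few sentences and one adjusted model, a somewhat smaller sample if earlier enrollees are excluded, and a more modest claim. No new data collection is needed.
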